8.1.3. Obtaining of patient's informed consent

An informed consent form, accompanied by a patient information leaflet in which the purpose of the blood samples collected will be clearly stated, will be signed by each patient before any data collection.

In addition, it will be mentioned that the histological samples taken at the diagnosis of the patients will be collected in order to constitute a bank of samples

A second informed consent form specific to the genetic analyses will be signed by each patient prior to all sampling.

8.1.4. Data collected in the individual case report form for each patient included (Appendix 3)

A) Data relating to the physician

- Surname, first name
- Gender
- Age
- Zip code, Town
- Public or private practice
- Type of contract

B) Screening form (only for cases)

- Visit screening date
- Consentment sign date
- Inclusion and non inclusion criteria
- Demographic data: month and year of birth (MM/AAAA)
- Data relating to the initial treatment of the patient: date of diagnosis of the initial renal cancer, date of diagnosis of renal cell carcinoma
- Data relating to the status of the patient in complete remission: Sunitinib start date, number and localization of metastatic sites at initiation of Sunitinib
- Blood samples during the screening visit: yes / no sampling and date of collection. If the samples are not available during the screening visit, a period of 6 weeks between screening and sampling will be allowed.
- Histological samples: date of sampling, type of sample, method of fixation.

C) Data collected at inclusion

For the cases

- Demographic data: age, gender, height, weight
- Data on the diagnosis of patients with metastatic renal cancer in complete remission: date of initial diagnosis of kidney cancer, date of diagnosis of metastatic renal cell carcinoma, nephrectomy (Yes / No), date of nephrectomy, type of nephrectomy; fixation method, OMS pathological classification, TNM classification 2009, Furhman nuclear grade, presence of necrosis, tumor size, presence or absence of a sarcomatoid embolus component
- Data relating to the state of the patient in CR at initiation of Sunitinib: initiation date, location of metastases, number of metastatic sites, prognostic classification MSKCC

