- Data on complete remission: date of complete remission; obtained by medical treatment alone or combined with local treatment, radiological assessment of complete remission, Therapeutic strategy after complete remission: continuation or discontinuation of treatment

For the controls

- Data relating to the inclusion and demographic data : consultation date ; demographic data : year of birth, age, sex, size, weight
- Data relating to the renal metastatic cancer initial treatment for a patient in complete remission : date of initial diagnosis of renal cancer, date of diagnosis of metastatic renal cancer, date of initiation of Sutent, nephrectomy (Yes/No), date and nephrectomy type, histology, OMS anatopathologic classification, TNM 2009 classification, Fuhrman nuclear grad, necrosis presence, vascular embolism, blood sample date before initiation of Sutent
- Data relating to a patient state with a mRCC before initiation of sunitinib: blood and histological sample (Yes/No) and sample date. If the sample are not available during the screening visit, un six week time limit between screening and inclusion visit is authorized metastasis localisation, number of metastasis, MSKCC prognostic classification

D) Data collected during follow-up visits

In this research, patient follow-up will be carried out over a period of 3 years, in accordance with the normal treatment procedures for this disease (visits every 2 to 3 months as per the expert opinion reported in the long-term diseases guide of the HAS).

For the cases

During the visit to diagnose possible disease progression, the following data will be recorded in the case report form:

- Date of the visit,
- Date of progression, progression type, for a known metastatic site or a new metastatic site
- Localization and number of metastatic sites
- Blood sample date
- treatment administered during progression

During the annual visit, following data will be recorded in the case report form:

- disease evolution
- treatment modification (temporary stop, definitive stop),
- No sample to be made

During the end of research visit (36 months after the inclusion visit), the following data will be recorded in the case report form :

- 36 months visit : Yes/No ; Date of the visit, treatment best answer post progression, duration of administration, local treatment associated

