- Last news : premature stop of the study ; date of latest news ; persistant remission complete since visit of inclusion ; complete remission after treatment of progression post RC ; progression of cancer ; number of subsequent line of treatment after Sutent
- Deaths (YES / NO), date of death

For the controls

During the follow-up visits at 6 and at 12 months, the following data will be recorded in the case report form :

- Data relating to a patient state with a mRCC at 6 and 12 months of treatment with Sutent : date of the visit, clinic evaluation with RECIST criteria, : response to the treatment, stability of the disease or progression, date of the progression, type of progression ; metastatic sites ; localization and number of metastatic sites ; blood sample and date of sample.

During the visit of progression: the following data will be recorded in the case report form :

- Data relating to a patient with a mRCC with a progression : date of the visit, date of progression, to a known metastatic site, new metastatic site, metastatic sites : localization and number of metastatic sites ; blood sample and sample date.

During the end of research visit (36 months after the inclusion visit), the following data will be recorded in the case report form :

- 36 months visit : Yes/No ; Date of the visit, treatment best answer after progression, duration of administration receives after progression with Sutent
- Last news : premature stop of the study ; date of latest news ; persistant remission complete since visit of inclusion ; complete remission after treatment of progression post RC ; progression of cancer ; number of subsequent line of treatment after Sutent
- Deaths (YES / NO), date of death

E) Centralized review of CT scans (only for patients in CR)

In this research, the CT scan data from patients in CR (CASES) will undergo a centralized of two of their scanner

- The scanner at baseline (at the initiation of sutent at first line)
- The scanner where the complete remission is present

This review will take place during the patient's screening visit. The latter will not be included until after the review of the CT scan, which will validate the complete response.

For this purpose, they should be burnt onto two CD-ROM :

- 1 CD-ROM for the scanner at baseline (at the initiation of Sutent in first line)
- 1 CD-ROM for the scanner where the complete remission is present

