8.2.3. Inclusion criteria

- Adult patients (≥ 18 years)
- Patients with mRCC confirmed by histological analysis
- Treated with Sunitinib according to a regimen in the text of the SmPC
- Presenting a complete remission in the preceding 5 years (according to RECIST v1.1) with Sunitinib only or combined with localized treatment (surgery, radiotherapy, cryoablation or radiofrequency ablation)
- Patients of childbearing age using a mandatory method of contraception
- Affiliated to a social security scheme
- Informed about the study methods and having given their consent

Exclusion criteria

- Complete remission occurring in the absence of treatment with Sunitinib

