- Visit (Yes/ No);
- Date of visit;
- Best response to treatment received post-progression;
- Duration of administration after progression with first-line Sunitinib;
- Last news: premature discontinuation of study, date of last news, persistent CR since inclusion visit, CR after treatment of post-CR progression, disease progression, number of subsequent lines after progression, post CR;
- Death (Yes/No), date of death.

For Controls

At the 6-month and 12-month follow-up visits of Sunitinib treatment:

- Date of visit;
- Clinical assessment using RECIST criteria (response to treatment, if progression: date of progression, progression at a known metastatic site or at a new site);
- Metastatic sites: location and number of metastatic sites;
- Blood sample and collection date.

If progression:

- Date of visit;
- Date of progression, type of progression (local or distant);
- Metastatic sites: location and number of metastatic sites;
- Blood sample and collection date

At the end-of-research visit (36 months after the inclusion visit):

- Visit (Yes/ No);
- Date of visit;
- Patient still treated with Sunitinib, if yes: response to treatment, if no: progression, new treatment, date of Sunitinib discontinuation;
- Number of subsequent treatment lines;
- Last news: study stopped prematurely, date of last news;
- Death (Yes/No), date of death.

Centralised review of Computerised Tomography Scan (CT Scan) - only for patients in CR

In this research, two of the scans of CR patients (Cases) will be reviewed centrally.

- The scan at initiation of first-line Sunitinib;
- The scan showing CR.

This review will take place between the screening visit and the inclusion visit of the patient. Thus a patient can only be included after the scans have been reviewed to validate the CR.

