6.3 Description of patients at inclusion

6.3.1 Demographical characteristics

Study population: Population of patients included

The demographic characteristics of the patients will be described by group and compared:

- Age (years);
- Sex (male/ female);
- Height (cm);
- Weight (kg).

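### Cases are weighed after complete remission and Controls around Sunitinib start, so the planned weight comparison cannot separate a difference present at Sunitinib start from later change

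*Protocol*

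**What the plan says.** **Cases.** Protocol 8.1.4 C lists, among the data collected at inclusion, "Demographic data: age, gender, height, weight". The Case CRF (Appendix 5) puts weight under the inclusion consultation date, outside the block on status at the start of Sunitinib. The Case items tied to Sunitinib start are "initiation date, location of metastases, number of metastatic sites, prognostic classification MSKCC"; weight is not among them.

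CR comes before inclusion. The eligibility criterion in Protocol 8.2.3 is "Presenting a complete remission in the preceding 5 years", and SAP 2.3 adds: "Thus a patient can only be included after the scans have been reviewed to validate the CR".

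**Controls.** Protocol 8.1.4 C lists "demographic data : year of birth, age, sex, size, weight", also at inclusion. Protocol 8.2.4 requires that Controls have had no Sunitinib before, and SAP 2.3 has them enrolled when it is initiated.

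**Analysis.** SAP 6.3.1 includes weight in kg in its list and states: "The demographic characteristics of the patients will be described by group and compared". SAP 4.1 sets a two-sided 5% level, with a t-test if the variable is judged normal and a Wilcoxon rank sum test otherwise. The Annex 1 template prints a p-value. The stated purpose (SAP 2.2.1) is to find factors associated with the occurrence of CR. SAP 6.3.2 has a separate group of variables described as of Sunitinib initiation, and weight is not in it. Neither document gives an adjustment or caveat for the time of weighing.

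**The concern.** The same CRF field holds values from two different points in the disease course. In Controls it is a value from around the start of treatment. In Cases it follows Sunitinib treatment and the outcome itself. The gap from Sunitinib start is the time to CR, on which the documents set no limit, plus up to 5 years from CR to inclusion.

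A factor associated with the occurrence of CR has to be measured before CR. If weight changes during treatment or remission, a group difference can appear where none existed at Sunitinib start, or a real one can be cancelled.

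Age and time since metastatic diagnosis share the mismatch, because SAP 5.2 counts both to inclusion. Both can be recomputed to Sunitinib start from dates already collected. Weight cannot, because the Case CRF asks for no weight from before Sunitinib.

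**Working it through.** **1. When each weight is taken**

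| | Cases | Controls |
|---|---|---|
| Visit at which weight is recorded | Inclusion | Inclusion |
| Position relative to Sunitinib start | After it, by the time to CR plus up to 5 years | Around it (inferred from no previous Sunitinib and enrolment at initiation) |
| Position relative to CR | After it | No CR has occurred |
| Weight at Sunitinib start on the CRF | None | The inclusion weight serves |

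**2. What the contrast contains**

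Observed difference = (difference at Sunitinib start) + (mean change in Cases from Sunitinib start to inclusion). Only the sum is observed, so the collected data cannot separate the two terms.

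**3. Reproducing the plan's figure**

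Inputs from SAP 2.5 and 4.1: 40 Cases, 80 Controls, two-sided 5%, d = 0.55, stated power 80%.

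Noncentrality = d / √(1/40 + 1/80) = d / √0.0375 = d / 0.1936. For d = 0.55 this is 2.84. With 118 degrees of freedom the noncentral t gives 80.4% power, and the smallest d with 80% power is 0.547. The plan's figure reproduces.

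**4. Rejection rate with no difference at Sunitinib start**

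The same function applies, with d replaced by an assumed mean shift s in Cases, in SD units, between Sunitinib start and inclusion. The documents give no value for s, so the range starts at zero.

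| s (SD) | Noncentrality s / 0.1936 | Rejection at 5% |
|---|---|---|
| 0 | 0 | 5% |
| 0.1 | 0.52 | 8.1% |
| 0.2 | 1.03 | 17.6% |
| 0.3 | 1.55 | 33.6% |
| 0.4 | 2.07 | 53.5% |

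For scale only, assume a weight SD of 12 to 18 kg, which is not in the documents. A 3 kg shift is then 0.25 to 0.17 SD and gives 25% to 14% rejection. A 5 kg shift is 0.42 to 0.28 SD and gives 57% to 30%.

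**5. Masking**

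If the true difference at Sunitinib start is d = 0.55 and Cases later shift by 0.3 SD the other way, the observed d is 0.55 − 0.30 = 0.25. The noncentrality is 1.29, and power falls from 80.4% to about 25%.

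**The case against.** **Size and direction are unknown.** Nothing in the documents says that weight changes, in which direction or by how much, and effects of treatment and of remission could offset each other. This stands. The rates above are illustrations, and zero belongs in the range.

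**The timing is visible.** SAP 6.3 is headed as a description at inclusion, and weight is kept out of the variables described as of Sunitinib start. This also stands: weight is not mislabelled. It is still tested for an objective that such a value cannot serve.

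**The consequence is narrow.** Weight is one of four demographic variables and one of many characteristics compared. It is not named as a hypothesised factor, and the SAP plans no multivariable model that it could enter. This limits the importance of the point.

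Some stronger readings are tempting but not supported:

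- *The test measures only the effect of treatment and remission.* The contrast also contains any difference at Sunitinib start. What fails is the separation of the two.
- *Cases are always weighed after central validation of the CR.* Protocol 8.1.4 E says of the patient: "The latter will not be included until after the review of the CT scan, which will validate the complete response". Protocol 8.2.5.2, however, has the inclusion questionnaire completed at the screening visit, when the scans are sent for review. The weight may therefore precede validation, though it still follows CR.
- *Controls are documented as weighed before the first dose with untreated disease.* The weighing date is not fixed anywhere; the 6-week tolerance on the CRF concerns sampling. Controls are excluded for previous systemic treatment, but earlier nephrectomy is allowed and recorded.
- *No Case can have a weight from before Sunitinib.* A Control who reaches CR moves to the Case group and would have one. The protocol expects no such patient, and the documents do not say which weight would be used.

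**Conclusion.** The concern holds in a limited form. Case weight follows Sunitinib and CR, while Control weight is taken around Sunitinib initiation. The SAP 6.3.1 weight comparison therefore cannot distinguish a difference present at Sunitinib start from later change, and its p-value should not be read as evidence of a factor associated with CR.

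The size depends on a shift that the documents do not give: from no effect on the 5% error rate at zero shift to about 54% rejection at 0.4 SD. These figures assume equal mean weights at Sunitinib start, a t-test and full recruitment of 40 and 80. That Controls are weighed around initiation is itself an inference from their eligibility and enrolment, though a reasonable one.

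The conclusion about interpretation does not depend on the size of the shift. Since one univariate comparison is affected, this is a cheap improvement and does not threaten the study as a whole.

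**What to change.** 1. Add one item to the Case CRF: the last weight in the medical file before the first Sunitinib dose, with its date.
2. In SAP 6.3.1, compare that value with the Controls' inclusion weight. Leave it missing if it is not found, in line with SAP 5.1, and do not substitute the inclusion weight. For a Control who moves to the Case group, apply the same rule.
3. Describe the Cases' inclusion weight for Cases only, without a test.
4. If the pre-Sunitinib weight cannot be collected or is largely missing, report weight by group descriptively, state the difference in timing, and leave weight out of the factors tested for CR.

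**Cost.** Steps 1 to 3 need one retrospective chart item for about 40 Cases, the matching protocol and eCRF change, and a short edit to SAP 6.3.1. Some values will be missing, possibly more often for older CRs, so the number missing should be shown. Step 4 needs only a change of SAP text.

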8.2. Setting

8.2.1. Population of physicians/health care professionals

The active participation of 15 - 20 oncologists ensures conditions of sufficient statistical accuracy to meet the objectives of the study.

Each physician will include patients with metastatic renal cell carcinoma in CR with Sunitinib (**Cases**).

The teams of [name] (IGR), of [name] (PPD) including doctors PPD and PPD , of [name] (PPD), of [name] (PPD), of [name] (PPD) will include 80 patients with metastatic renal cell carcinoma without CR at the start of Sunitinib administration. This is the control population. Given the rarity of the CR event observed (1.7%), it is expected that none of the patients in the control group (n = 80) will present CR with Sunitinib. **If any of the 80 controls present CR with Sunitinib during follow-up, s/he will be moved to the Cases group.**

These patients are seen in consultation and meet the inclusion and exclusion criteria.

The study's scientific committee has identified 25 sites that are likely to participate in this project. These sites have all been contacted (by email and by telephone) as part of a feasibility study (Appendix 14). At the end of this process, twenty sites have agreed to participate in the study.

If the evaluation of the number of patients that can be included by those 20 sites remains below 40 **Cases** and 80 **Controls**, the pool of participating physicians may be increased.

A description of the population of physicians will be made retrospectively on the basis of the identification data for the participating physicians (gender, age, location etc.).

In order to ensure the external validity of the study, it will then be verified that the population of participating physicians is representative of the total population of oncologists in France.

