8.1.2. Study schedule

The provisional schedule for the study is as follows:

- Submission of the protocol to the CCTIRS and the EC: November 2011
- Submission of the protocol to the French National Board of Physicians (CNOM): November 2011
- Submission of the protocol to the CNIL: February 2012
- Informing of the ANSM: November 2011
- Submission of the protocol to the Ministry of Research: November 2011
- Recruitment of participating physicians: September 2013 – June 2018

- Recruitment of patients: July 2014 – Until inclusion of all the patient in the study or later in December 2018
- End of follow-up: July 2014 – December 2021
- Database freeze and initial analysis: February 2022
- Final report: November 2022

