2.5 Number of patients required

The primary objective of the study is to describe the characteristics of mRCC patients achieving a CR with Sunitinib (Cases) and to compare them to the characteristics of metastatic renal cell carcinoma patients not achieving a CR with Sunitinib to identify factors associated with the occurrence of complete remission.

A sample size of N = 40 cases and N = 80 controls will provide a power of 80% in the detection:

- For continuous variable with a normal distribution, of an effect size (Cohen's d) ≥ 0.55 ;
- For a dichotomous variable, of a frequency difference between cases and controls corresponding to the ORs presented in the table below:

Frequency in controls	10%	20%	30%	40%	50%	60%	70%	80%	90%
Odds Ratio	≥ 4.33	≥ 3.27	≤ 0.19 or ≥ 3.16	≤ 0.26 or ≥ 3.12	≤ 0.29 or ≥ 3.44	≤ 0.32 or ≥ 3.78	≤ 0.32 or ≥ 5.29	≤ 0.31	≤ 0.23

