4 GENERAL CONSIDERATIONS FOR THE STATISTICAL ANALYSIS OF THE DATA

4.1 Statistical methods

The biostatistics department at AXIAL will perform the statistical analysis, with the exception of the analysis of biological data and biomarkers. Data will be analysed using SAS® software (version 9.4 or later - SAS Institute, North Carolina, USA).

Statistical tests will be carried out bilaterally at a 5% significance level (alpha).

Results will be presented in the form of tables per group (Cases/Controls) presenting:

- For quantitative parameters: number of patients (n), mean and standard deviation, minima and maxima, median and quartiles, and number of missing values.
- For qualitative parameters: number of patients, absolute and relative frequencies for each parameter modality, and number of missing values. Missing data will not be considered when calculating percentages.

Quantitative parameters will be compared between groups using the following methods: Beforehand, the distribution of the parameter will be checked graphically and by using Skewness and Kurtosis and Shapiro-Wilk statistics. If the distribution is considered normal, groups will be compared using a Student's t-test and the difference in means and the 95% Confidence Interval (CI) will be presented. If this is not the case, groups will be compared using a Wilcoxon rank sum test and Hodges-Lehmann estimator, with a presentation of the 95% CI.

For non-ordinal qualitative variables, groups will be compared using the Chi-2 test (or Fisher's exact test if the theoretical numbers <5) and the odds ratio will be presented when specified.

For ordinal qualitative variables, groups will be compared using the Cochran-Mantel-Haenszel test, ridit modified scores ('row mean score differ'). For ordinal qualitative count variables, groups will be compared using the Cochran-Mantel-Haenszel test, 'row mean score differ' table option.

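### Cases can come from about 20 sites and from earlier treatment years, Controls from five listed teams starting Sunitinib in about 2014 to 2018, and the pooled tests cannot separate a centre or era difference from a factor for CR

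*Protocol*

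**What the plan says.** **Where patients come from.** Protocol 8.2.1 says of Cases: "Each physician will include patients with metastatic renal cell carcinoma in CR with Sunitinib". It expects 15 to 20 oncologists and reports that twenty sites agreed to take part. For Controls, the same section lists five teams that "will include 80 patients with metastatic renal cell carcinoma without CR at the start of Sunitinib administration". SAP 2.3 repeats the five-team list. Appendix 11 still speaks of two control sites. Section 8.2.1 allows the physician pool to grow if numbers fall short, and the amendment log (Amendment 4) records that other centres were allowed to include Controls. Neither text ties control recruitment to the centres where Cases arise.

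**When they were treated.** Controls must not have had Sunitinib before (Protocol 8.2.4). Patient recruitment runs from July 2014 "Until inclusion of all the patient in the study or later in December 2018" (8.1.2). The criterion for Cases (8.2.3) is "Presenting a complete remission in the preceding 5 years (according to RECIST v1.1", so CR and the start of Sunitinib precede inclusion.

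**How they are compared.** SAP 4.1: "For non-ordinal qualitative variables, groups will be compared using the Chi-2 test", or Fisher's exact test for small expected counts. Quantitative variables get a t or Wilcoxon test. Ordinal variables get a Cochran-Mantel-Haenszel row-mean-score test with no stratifying variable named. SAP 6.3 applies these to all included patients. Neither document plans matching, stratification or adjustment for centre or calendar period.

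**The concern.** The primary objective is to identify factors associated with CR. A case-control comparison supports that only if the Controls represent the treated population from which the Cases came. Here the two groups can differ in hospital and in treatment period for reasons unrelated to CR.

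Several variables tested in SAP 6.3.2 can vary with local practice or calendar time: open or laparoscopic nephrectomy, adrenalectomy, lymph-node curettage, histological reporting, and which patients are chosen for Sunitinib. An unadjusted test shows only that the groups differ, not whether centre, era or CR is the reason. A centre or era difference would then be reported as an answer to the primary question.

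**Working it through.** **1. The plan's own figure.** SAP 2.5: "A sample size of N = 40 cases and N = 80 controls will provide a power of 80% in the detection" of d = 0.55. SAP 4.1: "Statistical tests will be carried out bilaterally at a 5% significance level (alpha"). The noncentrality is 0.55 / √(1/40 + 1/80) = 0.55 / 0.1936 = 2.84. The two-sided t test with 118 degrees of freedom then has power 80.4%, so the figure reproduces. It concerns random error only and gives no protection against the bias considered here.

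**2. The calendar gap.** Controls are Sunitinib-naive and enrolled from July 2014 to December 2018, so they start Sunitinib in about that period. This is inferred from two provisions; no section states it. For Cases, the amendment log shows that Amendment 3 (5 March 2015) widened the CR window from two to five years.
- Enrolled July 2014 under the two-year rule: CR from about July 2012.
- Enrolled March 2015 under the five-year rule: CR from about March 2010.

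The earliest admissible CR is therefore about March 2010, with Sunitinib started before that. The forms disagree on how early a start can be recorded: the Case inclusion page pre-prints 201_ for Sunitinib start, while the screening page allows any year from 2000.

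**3. Effect of a centre difference.** Assume a yes/no feature with no link to CR, present in 60% of patients in control-recruiting centres and in a fraction *e* elsewhere. Let *s* be the share of Cases from control-recruiting centres. Then:
- expected frequency in Controls = 0.60
- expected frequency in Cases, *q* = 0.60*s* + *e*(1 − *s*)
- expected OR = [*q*/(1 − *q*)] / [0.60/0.40]

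Example: *s* = 0.25 and *e* = 0.40 give *q* = 0.15 + 0.30 = 0.45, and OR = 0.818/1.5 = 0.55. The rejection rate is the exact binomial probability (80 Controls, 40 Cases) that the uncorrected chi-square p-value is at most 0.05.

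| Share *s* | *e* = 40%: *q*, OR, rejects | *e* = 50%: *q*, OR, rejects |
|---|---|---|
| 25% | 45%, 0.55, 34% | 52.5%, 0.74, 12% |
| 50% | 50%, 0.67, 18% | 55%, 0.82, 8% |
| 75% | 55%, 0.82, 8% | 57.5%, 0.90, 6% |
| 90% | 58%, 0.92, 5.5% | 59%, 0.96, 5% |
| 100% | 60%, 1.00, 5% | 60%, 1.00, 5% |

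A 25% share is what equal recruitment per site would give (5 of 20 sites). The frequencies and shares are all assumptions.

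**4. Effect of an era difference.** If calendar time shifts a continuous variable by 0.1, 0.2 or 0.3 SD between the groups (assumed), the planned t test rejects 8%, 18% or 34% of the time.

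**5. What a within-centre comparison can resolve.** Suppose 10 or 20 of the 40 Cases come from centres with Controls, and all 80 Controls contribute. For d = 0.55 the noncentrality is 0.55/√(1/10 + 1/80) = 1.64 or 0.55/√(1/20 + 1/80) = 2.20, and power is 37% or 59%. Splitting into strata will not improve on this.

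**The case against.** **The centre sets overlap.** The five teams are also participating physicians and may enrol Cases. The amendment log records that the cap of two Cases per centre was lifted and that further centres could recruit Controls. A reader might infer that Cases and Controls come from different hospitals; the text does not say so. This stands: the share of overlap is unknown, and at 75% or more the table shows rejection of 8% or less.

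**The era gap is easily exaggerated.** From the five-year window alone, a reader might infer that a Case enrolled in 2014 could have had a CR in 2009. The amendment dates rule that out. A gap of some years remains possible.

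**Coding is partly standardised.** The protocol prescribes TNM 2009, the WHO classification and Fuhrman grade for both groups, which weakens histology and staging as examples. The surgical sub-items apply only to patients with a nephrectomy and follow the date of that operation, so adjusting them for year of Sunitinib start would miss the point. Both remarks are fair.

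**Is there another safeguard?** The comparison of physicians with national data (Protocol 8.2.1, SAP 6.2) addresses representativeness. It does nothing to balance Cases against Controls.

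**Conclusion.** The concern holds as a possibility that the plan leaves unexamined. Controls are assigned to a narrower set of teams and to a later start of treatment than Cases need have, and every planned comparison is pooled and unadjusted.

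For the assumed binary feature, the chance of a false finding runs from the nominal 5% to about 34%, depending mainly on the unknown share of Cases from control-recruiting centres. It would be tempting to quote 34% as the plan's error rate, or to say that the groups do differ by centre or era. The documents support neither: the upper figure needs both a 20-point contrast and only a quarter of Cases from shared centres. The sample size is not wrong; it does not address this question.

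**What to change.** Amend SAP 4.1 and 6.3 before analysis:

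- **(a)** Tabulate Cases and Controls by centre and by year of Sunitinib start. This shows at once how far the groups overlap.
- **(b)** Beside each unadjusted result, print a pre-specified sensitivity analysis stratified by centre: a Mantel-Haenszel odds ratio for binary factors and a van Elteren test for quantitative or ordinal ones. Only centres with both groups contribute; state how many Cases that leaves.
- **(c)** Where start years overlap, add an estimate adjusted for year of Sunitinib start, or year of nephrectomy for the surgical items.
- **(d)** Where an estimate moves materially toward the null under (b) or (c), describe the factor as possibly explained by centre or era. Do not require significance or agreement in the reduced sample, since with few Cases that would discard real factors by chance.

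Do not restrict to Cases who started Sunitinib within the Controls' period. Such Cases must have reached CR before enrolment closed, so the restriction selects fast responders and adds a new bias.

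**Cost.** SAP text and extra table columns. Sunitinib start date is on the forms for both groups; site number is on the Control form, and enrolling site is on the sample handover form used for both. The price is imprecision, with power of about 37% to 59% for d = 0.55 if 10 to 20 Cases contribute. Where centres or years barely overlap, adjustment cannot separate them from Case status, and the report should say so.
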